Statistical Design and Power

Study Title: DadSpace: Increasing Community Support Resources for Perinatal Fathers

Study ID: 1754

Date of Plan: 6/14/2021

Statistical Design and Power

We anticipate that by the conclusion of the DadSpace program feasibility trial, 28 fathers will have completed the program as well as pretests and posttests, and 28 fathers will have completed pre- and posttests as wait-list controls. With a moderate effect size of Cohen's $d = .50$, this sample size will provide power = .95 using a 2 (time) by 2 (group) repeated measures ANOVA with stability coefficients of $r = .50$. Power will be lower but still sufficient (.81) to detect a small/moderate effect size of $d = .33$. Given that pilot trials of DadSpace (e.g., *Becoming Fathers*) and focus groups have indicated that DadSpace is likely to be effective, we believe that effect sizes of .40-.50 are likely on each of the primary outcome measures.

In section 4.2, we entered multiple "additional measures," all of which assess program implementation. These measures provide us with feedback as to how the DadSpace program was delivered and received by the participants. Following best practices (e.g., Berkel et al., 2011), this information will serve two purposes: to provide guidance on strengthening the DadSpace program, and to assess how variations in implementation are related to degree of program impact. In order to assess the latter, exploratory correlational analyses will be conducted between implementation variables and gain scores on the pre-/posttest measures of program impact.

<https://doi.org/10.1007/s11121-010-0186-1>

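### The stated powers (.95 at d = .50, .81 at d = .33) cannot both be right, and the group-by-time test has about .45 and .23 at those effects

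*SAP*

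**What the plan says.** The SAP, Statistical Design and Power, anticipates that "28 fathers will have completed the program as well as pretests and posttests" and that "28 fathers will have completed pre- and posttests as wait-list controls". For d = .50 it says that "this sample size will provide power = .95 using a 2 (time) by 2 (group) repeated measures ANOVA with stability coefficients of" r = .50. It continues: "Power will be lower but still sufficient (.81) to detect a small/moderate effect size of" d = .33. On the effects to be expected it says "we believe that effect sizes of .40-.50 are likely on each of the primary outcome measures".

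The SAP gives no alpha and no sidedness. It does not name the ANOVA term being tested, and it does not say which contrast d describes. The protocol gives an anticipated total of 56 (Participant Population) and no power calculation. It lists the effect of the mentoring program on fathers' short-term outcomes as a primary objective (Study 1 Objective 2, under the purpose of the project).

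**The concern.** Power of .95 for a half-SD effect with 28 per arm is far above what a two-arm comparison of change scores gives at r = .50. The fall from .95 to .81 is also too shallow for an effect that shrinks by a third.

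At stake is what the trial can say about Objective 2. If power at the expected effects is below one half, a real effect of that size is more likely to be missed than found. A reader who took the .95 at face value could then mistake a null result for evidence that the program does not work. The protocol's data preservation section says the findings are expected to help secure a larger grant, so a wrong power statement could mislead beyond this trial.

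**Working it through.** **Inputs.** From the SAP: n = 28 per arm (N = 56), r = .50, two time points, two groups, d = .50 and d = .33, expected effect .40-.50. Assumed, because not stated: alpha .05 two-sided, and d as the between-arm difference in pre-post change in SD units.

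**1. Trying to reproduce the stated figures.** Enter f = d/2 as the interaction effect in the repeated measures ANOVA, with λ = f² × N × 2 / (1 − r) and F(1, 54).

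- d = .50: f = .25, λ = .0625 × 56 × 2 / .5 = 14.0, power .957. This matches .95.
- d = .33: f = .165, λ = .027225 × 224 = 6.10, power .679. This does not match .81.

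A pre-post time effect in all 56 fathers pooled gives the same power, because the noncentrality is d√56 and 56 × .25 = 14. That test does not compare the arms.

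**2. What f = .25 means.** Every cell deviates by .25 SD from the no-interaction pattern. One arm moves up .5 SD and the other down .5 SD, so the arms differ in change by 1.0 SD. Check: (1.0 × √14)² = 14, the same λ.

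**3. Power of the program test at the stated effects.** With two time points, the group-by-time F(1, 54) equals a t-test on gain scores. The gain SD is √(2(1 − .5)) = 1.0 SD, so it does not matter whether d is scaled by the raw SD or the gain SD. The noncentrality is d × √(28/2) = d × 3.742.

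| d | Noncentrality | Power, two-sided .05 | SAP |
|---|---|---|---|
| .50 | 1.87 | .451 | .95 |
| .40 | 1.50 | .312 | not given |
| .33 | 1.23 | .228 | .81 |

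Simulation with 100,000 runs gave .452 at d = .50 and .228 at d = .33.

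**4. Whether the two figures can coexist.** With n, r and the test fixed, the noncentrality is proportional to d, whatever d means. At two-sided .05 with 54 df:

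- Power .95 needs noncentrality 3.67. At d = .33 that becomes 3.67 × .33/.50 = 2.42, which gives power .66.
- Power .81 needs noncentrality 2.89. At d = .50 that becomes 2.89 × .50/.33 = 4.38, which gives power .99.

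Changing alpha does not help. In the normal approximation (lower tail ignored), with critical value c, both figures hold only if .66(c + 1.645) = c + .878. That gives c = .61, a two-sided alpha of about .5.

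**5. Sensitivity of the program test (d = .50 / d = .33).**

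| Variant | Power |
|---|---|
| One-sided .05, gain scores | .58 / .34 |
| Pretest as covariate, two-sided | .56 / .29 |
| Pretest as covariate, one-sided | .69 / .41 |
| r = .3 | .34 / .18 |
| r = .7 | .66 / .35 |

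**6. What the sample can do.** The effect detectable with 80% power is .76 SD. The expected 95% CI half-width is about 2.00 × √(2/28) = .54 SD. Power .95 at d = .50 needs 105 per arm, and .81 at d = .33 needs 149 per arm. Power .80 needs 64 and 146 per arm.

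**The case against.** The strongest reply is that the SAP leaves alpha, sidedness, the tested term and d undefined, so .45 and .23 are conditional figures. That stands, and the conditions belong with the numbers. It does not rescue the plan. If d = .50 was meant as f = .25, the effect is a 1.0 SD difference in change, which is not moderate, and the second figure is still .68. The inconsistency between the two powers does not depend on how d is defined.

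The protocol has four outcome surveys (Online Surveys), so more time points might have been used. On the f = d/2 route, three or four time points give .77 or .84 at d = .33, but .99 or above at d = .50. The pair still does not appear, and the SAP specifies two time points.

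It can also be said that this is a feasibility pilot, that 28 per arm is presented as an anticipated number and not derived from the power, and that nothing says how a null result will be read. All of that is fair. The sample size is not being criticised, and the consequences described above are risks, not certainties. But effectiveness is labelled a primary objective, and a small pilot still needs a correct statement of its power.

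**Conclusion.** The concern holds. Without any assumption about d, the two stated powers cannot come from one calculation with the stated n and r at any conventional alpha, so at least one is wrong. With d as the between-arm difference in change and two-sided alpha .05, both are wrong: .45 against .95, and .23 against .81. Across the SAP's expected range of .40-.50, power is .31 to .45, so an effect of that size would be missed more often than found. The most favourable alternative checked at r = .50 (pretest as covariate, one-sided) reaches only .69 and .41.

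These figures assume 28 independent completers per arm and one outcome. The anticipated total of 56 equals the 28 + 28 completers, so no dropout is allowed for. Dropout, clustering within mentoring groups, or any multiplicity adjustment would lower power further.

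**What to change.** State alpha, sidedness, the ANOVA term that tests the program, and what d standardises. Then replace both power figures. If the sponsor confirms the assumptions used here, the text could read:

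*With 28 completers per arm, a pre-post correlation of .50 and two-sided alpha .05, the group-by-time test has power .45 for a between-arm difference in change of .50 SD and .23 for .33 SD; 80% power requires a difference of .76 SD. These figures make no allowance for dropout, clustering within mentoring groups or multiple outcomes.*

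Delete the description of the power as sufficient.

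Two options go beyond the correction. Objective 2 could be reported mainly as estimates with 95% confidence intervals (expected half-width about .54 SD), which suits a feasibility trial. Alternatively, the pretest could be used as a covariate. Power would then be .56 and .29, with .66 SD detectable at 80% power. Either would change how a primary objective is analysed or reported, so the sponsor must decide.

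The core correction costs only SAP wording. The stated power becomes less favourable, and no procedure or sample size changes.

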Describe the purpose for the proposed project.

We are building on previous work to identify opportunities to meet the needs of perinatal fathers. The term perinatal encompasses the time leading up to and immediately following the birth of a child. Father involvement in child rearing is beneficial to mothers and children, but fathers are routinely overlooked by available support opportunities at the transition to parenthood. Our pilot project seeks to apply research evidence and best practices to address the disparity in socioemotional community support and education programs serving perinatal fathers. In a previous pilot study, we learned from fathers participating in focus groups that they are interested in opportunities to connect with other fathers in the same life stage to talk about their experiences and learn from each other. We also learned that fathers worry about meeting varied role expectations, that available resources tend to overlook the unique experiences of fathers, and that it can be challenging to find quality information in a digital world saturated with conflicting information about parenting. This project seeks to address these primary issues through community-based, father-centric support and educational programs. WCNC education staff will facilitate a discussion-based group mentoring program for fathers who are expecting or recently had a baby. This program seeks to increase connection with other fathers, reduce stress related to parenting a baby, and increase parenting confidence. We plan to evaluate the feasibility of the program through satisfaction surveys and other measures of the program's implementation. We also plan to evaluate the effectiveness of the program by providing participants with surveys asking about their well-being, knowledge, confidence in parenting, and their satisfaction with their social networks. We are additionally developing educational podcasts focused on topics relevant to prenatal and postpartum fathers, which will be evaluated as a supplementary component to the mentoring program. Our research objectives are the following: Study 1 Objective 1 (Primary): We seek to determine the feasibility and acceptability of a program targeting perinatal fathers offered in a community clinic setting. Study 1 Objective 2 (Primary): Examine whether participating in a discussion-based group mentoring program increases the likelihood of positive short-term outcomes for fathers. Study 1 Objective 3 (Secondary): Identify whether listening to brief, targeted educational podcasts predicts increased positive outcomes for fathers over and above the mentoring group alone. Study 2 Objective 1 (Primary): Identify whether participants who listen to brief,

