Where and when will this procedure take place?

Participants will be recruited from the pool of people who have signed up for the mentoring group through WCNC. WCNC will advertise the mentoring group through their website and marketing materials as they do for other education classes they offer. Fathers who sign up for or express interest in the group program will be provided information about the associated research study by information posted on the WCNC website or by WCNC staff through verbal interaction, emails and/or flyers handed out at the clinic. Social media (e.g., Instagram/Facebook) postings made by department and clinic accounts will also be used to promote the study. Participation in the study is not required for those attending the mentoring group. Fathers attending the mentoring groups will be provided with links to listen to podcast episodes. Podcast listeners who have consented to participate in the study will be invited through the podcast website to complete brief satisfaction surveys about each podcast episode using their study ID.

Who will conduct this procedure?

Personnel

[name]

External User

Personnel
[name]

External User

Personnel
[name]

External User

Indicate the frequency and duration of visits/sessions as well as the subject's total time commitment for the study.

Describe how the data will be collected (i.e. in person or online).

Sign-ups for mentoring groups will occur online through the WCNC website.

Will any video, photography, or audio be recorded as part of this procedure?

No

Will data be collected anonymously?

No

Procedure Description
Screening and Consent

This procedure is:

Research Activity Involving Participants, Participants Data, or Biospecimens

This procedure is:

Where and when will this procedure take place?

All those who have decided to take part in the mentoring groups will be assigned an ID by WCNC staff. Potential participants will use this ID to complete an online screener survey. Those who are eligible will then be automatically provided consent information online through Qualtrics. Research staff will notify WCNC staff of the ID numbers of consented participants for management of survey distribution.

Who will conduct this procedure?

Personnel

[name]

Personnel

[name]

External User

Indicate the frequency and duration of visits/sessions as well as the subject's total time commitment for the study.

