Completing the online screening and consent procedure will take 5-15 minutes.

Describe how the data will be collected (i.e. in person or online).

Online

Will any video, photography, or audio be recorded as part of this procedure?

No

Will data be collected anonymously?

No

Procedure Description

Participation in the Mentoring Program

This procedure is:

Research Activity Involving Participants, Participants Data, or Biospecimens

This procedure is:

Where and when will this procedure take place?

Program facilitation will be conducted by trained staff members ([name], [name]) through WCNC – either in-person at clinic facilities or virtually by Zoom depending on health guidelines. Programs will start running in August, 2021, with a new group starting each month.

Who will conduct this procedure?

Personnel

[name]

External User

Personnel

[name]

External User

Indicate the frequency and duration of visits/sessions as well as the subject's total time commitment for the study.

1.5 hours per session, with 8 total sessions. Total time: 12 hours.

Describe how the data will be collected (i.e. in person or online).

Facilitators will be asked to keep attendance data, rate participant engagement, and complete a checklist of program items completed for each week of the intervention. At the end of the mentoring program, facilitators will also be asked to provide their feedback about the supportiveness of the group dynamics.

Will any video, photography, or audio be recorded as part of this procedure?

No

Will data be collected anonymously?

No

Procedure Description

Online Surveys

This procedure is:

Research Activity Involving Participants, Participants Data, or Biospecimens

This procedure is:

Experimental

Where and when will this procedure take place?

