Any contact with participants to provide referrals will be noted and tracked by the staff member.

Will any video, photography, or audio be recorded as part of this procedure?

No

Will data be collected anonymously?

No

Privacy and Confidentiality

Explain how the established data management plan along with consent processes and other elements of the research design address the following.

Privacy is considered from the perspective of the participant and is a right to be protected. Privacy refers to an individual's interest in controlling others' access to themselves.

Based on their privacy interests, participants may want to control:

- The time and place where they give information
- The nature of the information they give
- Who receives and can use the information

For example, persons might not want to be seen entering a place that might stigmatize them, such as a pregnancy-counseling center identified as such by signs on the front of the building.

Describe how you will protect subject's privacy.

Participants will be able to complete electronic surveys in locations they are comfortable with, as chosen by the participant. Participants who attend the small-group mentoring program will be associating with a business they have already chosen to be affiliated with prior to being recruited for the study. If a participant is not comfortable attending the program due to its location or the other group participants, they may choose to stop attending the mentoring program at any time. Participants who complete the podcast survey will be able to provide their responses anonymously.

Confidentiality is about data. Confidentiality pertains to protecting information from disclosure based on an agreement between the participant and the researcher. When an individual shares information in a relationship of trust and expects it to be kept private or will be disclosed only with specific permissions, researchers must uphold this agreement and maintain data appropriately.

Describe how you will maintain the confidentiality of subjects' information.

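### The SAP's only stated test of the program effect, and its .95 power, treat program fathers as independent although they are mentored in groups; on the monthly schedule the likely error is modest

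*SAP*

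**What the plan says.** The SAP (Statistical Design and Power) expects that "28 fathers will have completed the program as well as pretests and posttests", with another 28 fathers assessed as wait-list controls. It computes power "using a 2 (time) by 2 (group) repeated measures ANOVA", giving .95 at d = .50 with a stability coefficient of .50. In that design the group factor is program versus wait-list. The only dependence allowed for is between one father's pretest and posttest. No ICC, design effect or mentoring-group term appears.

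The Protocol's purpose statement lists the program effect as a primary objective: "Study 1 Objective 2 (Primary): Examine whether participating in a discussion-based group mentoring program" improves short-term outcomes. Delivery is collective. Under Participation in the Mentoring Program there are 8 sessions of 1.5 hours, and "Programs will start running in August, 2021, with a new group starting each month". The Privacy and Confidentiality section refers to "Participants who attend the small-group mentoring program". More connection among fathers is itself a stated aim.

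Two procedures suggest that group membership can be recovered: "Facilitators will be asked to keep attendance data" and "All those who have decided to take part in the mentoring groups will be assigned an ID by WCNC staff".

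**The concern.** Fathers in one mentoring group share a facilitator, the same sessions and each other's company, and that interaction is part of how the program is meant to work. Some correlation of gains within a group is therefore plausible. A repeated measures ANOVA with a father-level error term ignores it, so the standard error of the group-by-time effect is too small for any positive correlation. Intervals would be too narrow and the test would reject too often. This ANOVA is the only test the SAP names for a primary objective, and the Protocol expects the findings to support a larger grant application, so overstated precision would carry forward.

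**Working it through.** **Inputs from the documents:** 28 program and 28 wait-list fathers, d = .50, r = .50, stated power .95 (SAP); monthly group starts from August 2021, 8 sessions, proposed end date July 30, 2022 (Protocol).

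**Assumptions, not in the documents:** two-sided 5% test; ICC of gains .05 to .10, with .01 as a low case; wait-list fathers unclustered.

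**Step 1: reproduce the .95.** With f = d/2 = .25, the noncentrality is N × f² × 2/(1 − r) = 56 × .0625 × 2/.5 = 14. On (1, 54) degrees of freedom, power is .957. No term in this formula allows for mentoring groups. The same formula gives .68 at d = .33, where the SAP states .81, so the power comparisons below hold only on the reading that reproduces the .95.

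**Step 2: number of groups.** Four surveys four weeks apart span 12 weeks. To end by July 30, 2022, a father must start by about May 7, 2022. Monthly starts from August to April or early May give 9 or 10 groups, that is, about 28/9 = 3.1 or 28/10 = 2.8 study fathers per group.

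**Step 3: standard error.** With group sizes m in the program arm only, the true standard error divided by the independence standard error is √{[2 + (Σm²/28 − 1) × ICC]/2}.

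- 10 groups (eight of 3, two of 2): Σm² = 80, so the bracket term is 1.857 and the ratio is 1.023 at ICC .05 and 1.045 at .10.
- 9 near-even groups (eight of 3, one of 4): Σm² = 88, term 2.143, ratio 1.026 and 1.052.
- 4 groups of 7: Σm² = 196, term 6, ratio 1.072 and 1.140.

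**Step 4: type I error of the SAP's ANOVA.** For two time points, the group-by-time test is the pooled t-test on gains. Simulated with gain SD 1 and 400,000 runs per cell:

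| Groups among the 28 fathers | ICC .01 | ICC .05 | ICC .10 |
|---|---|---|---|
| 10 groups of 2–3 | .051 | .055 | .061 |
| 9 groups of 3–4 | .051 | .056 | .062 |
| 9 uneven (1,2,2,3,3,3,4,5,5) | .052 | .058 | .065 |
| 7 groups of 4 | .052 | .059 | .067 |
| 5 uneven (3,4,6,7,8) | .053 | .065 | .081 |
| 4 groups of 7 | .054 | .068 | .086 |

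**Step 5: do the alternatives work?** Comparing the mean of the mentoring-group means with the wait-list fathers, with Satterthwaite degrees of freedom, gives a type I error of .049 to .056 in every cell of that table. A random-effect model was run (100,000 runs) for two balanced layouts. At ICC .05 and .10 its type I error is .043 and .045 for 7 groups of 4, and .041 and .045 for 4 groups of 7. It estimates the group variance as zero in 34–46% of runs.

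**Step 6: power at noncentrality 14.** For the group-mean test:

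| Groups | ICC 0 | ICC .05 | ICC .10 |
|---|---|---|---|
| 10 groups of 2–3 | .946 | .937 | .926 |
| 9 groups of 3–4 | .945 | .934 | .921 |
| 9 uneven | .916 | .902 | .893 |
| 7 groups of 4 | .942 | .925 | .901 |
| 4 groups of 7 | .909 | .852 | .798 |

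At ICC .05 and .10 the random-effect model gives .921 and .898 for 7 groups of 4, and .848 and .794 for 4 groups of 7.

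**The case against.** The strongest reply is about size. On the monthly schedule the excess type I error is around one percentage point. It rests on an assumed ICC, in a pilot that also has feasibility as a primary objective. That stands, and it limits the severity.

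A reader might also infer that clustering overturns the .95 and leaves the study underpowered. The calculations do not support this. With 9 or 10 near-even groups at ICC .05 to .10, the SAP's own ANOVA still rejects .948 to .954 of the time at noncentrality 14, at a slightly inflated type I error. The lower powers in the second table come from replacing the test.

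The group-mean test has its own costs. With nine uneven groups its power is .916 even at ICC zero, against .957 for the ANOVA, and it gives a group with one study father the same weight as a group of five. That stands too, and it is why the test is proposed below as a check and not as the main analysis.

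Finally, the Protocol names Mplus as example software, and the SAP refers to a section 4.2 that is not supplied, as the Protocol's attachments are not. Multilevel modelling is therefore not excluded. But neither the software mention nor anything in the supplied text specifies a mentoring-group term, so the gap in the stated analysis remains.

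**Conclusion.** The point holds as a gap in specification, conditional on gains being positively correlated within mentoring groups. The direction is certain under that condition; the size is not, because the documents give no ICC, group size or alpha. For an ICC of .05 to .10 and a two-sided 5% test, the type I error is about .055 to .065 with 9 or 10 groups. The true standard error is about 2–5% larger than the ANOVA's if those groups are near even. With only four groups of 7 the type I error is about .07 to .09, and at ICC .01 the problem is negligible.

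Two stronger readings are not supported. One is that false positives roughly double: that needs a few large groups and a higher ICC (about .125 with four groups of 7 at ICC .20), whereas the documented schedule points to more and smaller groups. The other is that group membership will be lost: attendance records and clinic-assigned IDs suggest that it can be recovered, although the plan does not say it will reach the analysis dataset. Severity is minor to moderate.

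**What to change.** - Carry a mentoring-group ID into the analysis dataset. The Protocol gives research staff only participant IDs and survey data, so the clinic would need to pass on a group code.
- Test the program effect on gains with a partially nested mixed model: a random mentoring-group effect in the program arm only, with small-sample degrees of freedom.
- Report the group-mean comparison with Satterthwaite degrees of freedom as a check, noting that it weights groups equally, not fathers.
- State in the SAP that the .95 assumes independent fathers.

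The cost is SAP wording, one variable and somewhat wider intervals. For the group-mean test the degrees of freedom fall from 54 to about 21–26 with 9 or 10 groups, or about 9–10 with four. On the SAP's own noncentrality, at ICC .05 to .10, its power is about .92–.94 with 9 or 10 even groups, .89–.90 with nine uneven groups and .80–.85 with four. The mixed model is slightly conservative when groups are few.
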